16. TRIAL CLOSURE

16.1. End of Trial

For regulatory purposes the end of the trial will be when the final data item for the final patient is received by the UCL CTC (i.e. it is anticipated that this will be when the final patient completes their 2 year follow-up visit). At this point the 'declaration of end of trial' form will be submitted to the MHRA and Ethics Committee, as required.

Following this, UCL CTC will advise sites on the procedure for closing the trial at the site.

Once the end of trial has been declared, no more prospective patient data will be collected but sites must co-operate with any data queries regarding existing data to allow for analysis and publication of results.

16.2. Archiving of Trial Documentation

At the end of the trial, UCL CTC will archive securely all centrally held trial related documentation for a minimum of 5 years. Arrangements for confidential destruction will then be made. It is the responsibility of PIs to ensure data and all essential documents relating to the trial held at site are retained securely for a minimum of 5 years after the end of the trial, and in accordance with national legislation.

Essential documents are those which enable both the conduct of the trial and the quality of the data produced to be evaluated and show whether the site complied with the principles of GCP and all applicable regulatory requirements.

UCL CTC will notify sites when trial documentation held at sites may be archived. All archived documents must continue to be available for inspection by appropriate authorities upon request.

16.3. Early Discontinuation of Trial

The trial may be stopped before completion as an Urgent Safety Measure on the recommendation of the TSC or IDMC (see section 14.5.2 Trial Steering Committee (TSC) and 14.5.3 Independent Data Monitoring Committee (IDMC)). Sites will be informed in writing by UCL CTC of reasons for early closure and the actions to be taken with regards the treatment and follow up of patients.

16.4. Withdrawal from Trial Participation by a Site

Should a site choose to close to recruitment the PI must inform UCL CTC in writing. Follow up as per protocol must continue for any patients recruited into the trial at that site and other responsibilities continue as per the mNCA.

17. STATISTICS

17.1. Sample Size Calculation

The primary endpoint is the overall response rate (defined as complete response (CR), very good partial response (VGPR), partial response (PR) or minor response (MR) i.e. a greater than 25% reduction in the serum IgM level) by 24 weeks post commencing treatment.

It is thought the response rate could be around 60% but a rate of more than 40% is needed for this combination to be taken forward into a larger study. Using an A'Hern phase II trial design with a 1-sided alpha of 0.05 and power of 80% we will require 42 patients. The primary endpoint will be met if we see 23 or more responses.

17.2. Statistical analysis

17.2.1. Analysis of primary endpoint

The primary endpoint is the overall response rate (defined as complete response (CR), very good partial response (VGPR), partial response (PR) or minor response (MR) i.e. a greater than 25% reduction in the serum IgM level) by week 24 post commencing treatment. This will be presented as a percentage with 90% confidence interval. We do not expect missing response data at this time point (in this patient population) to be a problem, however, if it occurs it will be treated in the following way:

Response data before 24 weeks	24 week response	Clinical status at week 24	Response
Response reported at an earlier time point	Missing	Alive with no progression reported	Responder
No response at earlier time points	Missing	Any	Non responder
Any	Missing	Progressed or died	Non responder

Any patient who does not start trial treatment will be excluded and replaced.

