3.1. Trial Objectives

3.1.1. Primary Objective

- To determine the efficacy (overall response rate at 24 weeks) of the combination of rituximab and pembrolizumab in relapsed/refractory WM

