9.2.1. Assessments prior to each cycle of treatment

The following assessments should be performed within 3 days prior to each cycle:

- Clinical examination: physical examination (including assessment of lymph node, liver and spleen size)
- Concurrent medication assessment
- Adverse event assessment
- Observations: pulse, temperature, blood pressure, oxygen saturations
- Weight
- Assessment of ECOG performance status (see appendix 3)
- Full blood count (including red blood cell (RBC), haemoglobin (Hb), white blood cell (WBC) absolute neutrophil count (ANC), absolute lymphocyte count (ALC), haematocrit and platelets)
- Biochemistry (including bicarbonate, uric acid, albumin, alkaline phosphatase (ALP), alanine/aspartate transaminase (ALT/AST), total bilirubin, calcium, creatinine, potassium, sodium, glucose, urea, and estimated glomerular filtration rate (eGFR), U&E, liver function tests (LFT), and amylase)
- Electrocardiogram (ECG)
- Serum IgM, IgG and IgA
- Serum paraprotein
- Serum immunofixation (only to be performed if paraprotein not detectable)
- TSH, glucose and ACTH tests
- Highly sensitive urine or serum pregnancy test in women of childbearing potential (WOCBP)

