APPENDIX 3: RESPONSE ASSESSMENT*

Response category	Definition
Complete response (CR)	
 • Absence of serum monoclonal IgM protein by immunofixation • Normal serum IgM level^a • Complete resolution of lymphadenopathy and splenomegaly if present at baseline • Morphologically normal bone marrow aspirate and trephine biopsy
Very Good Partial Response (VGPR)	
 • Detectable monoclonal IgM protein • $\geq 90\%$ reduction in serum IgM level from baseline^b • Complete resolution of extramedullary disease, i.e. lymphadenopathy/splenomegaly if present at baseline • No new signs or symptoms of active disease
Partial response (PR)	
 • Detectable monoclonal IgM protein • $\geq 50\%$ but $<90\%$ reduction in serum IgM level from baseline^b • Reduction in extramedullary disease, i.e. lymphadenopathy/splenomegaly if present at baseline • No new signs or symptoms of active disease
Minor response (MR)	
 • Detectable monoclonal IgM protein • $\geq 25\%$ but $<50\%$ reduction in serum IgM level from baseline^b • No new signs or symptoms of active disease
Stable disease (SD)	
 • Detectable monoclonal IgM protein • $<25\%$ reduction and $<25\%$ increase in serum IgM level from baseline^b • No progression in extramedullary disease, i.e. lymphadenopathy/splenomegaly • No new signs or symptoms of active disease
Progressive disease (PD)	
 • $\geq 25\%$ increase in serum IgM level^{a,b} from lowest nadir^c and/or • Progression in clinical features attributable to the disease

*Owen et al, 2013

^aIgM responses/progression should be confirmed by a second measurement (ideally taken within the same cycle as the initial measurement)

^bSequential changes in IgM levels may be determined either by IgM protein quantitation by densitometry or total serum IgM quantitation by nephelometry

^cThe effects of any plasmapheresis should be considered when determining the lowest nadir

Note: where local investigations are inconclusive in determining progression, or the Site are uncertain that the progression in clinical features is attributable to the disease, the TMG should be contacted for advice. In these circumstances please email [contact].

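### If the primary endpoint is response at 24 weeks, row 1 of the missing-data table can count a minor response that a later IgM shows was already lost

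*Combined protocol and SAP*

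**What the plan says.** The missing-data table in section 17.2.1 has three rows for a missing week-24 response.

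- Row 1 gives responder when the record shows "Response reported at an earlier time point" and the week-24 status is "Alive with no progression reported".
- Row 2 gives non-responder when there was no earlier response, whatever the status.
- Row 3 gives non-responder when the patient has progressed or died, whatever came before.

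No row refers to the most recent IgM.

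The timing of the endpoint differs between sections. The primary objective (3.1.1) is the "overall response rate at 24 weeks", and sections 1.1 and 3.2.1 also place the response *at* 24 weeks. Sections 17.1 and 17.2.1 define it as response *by* 24 weeks.

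In Appendix 3, a minor response is a fall in IgM from baseline of at least 25% but under 50%. IgM progression is a rise of at least 25% measured "from lowest nadir". A footnote asks for IgM responses and progression to be confirmed by a second measurement.

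Formal response assessments fall at 12 weeks, 24 weeks and 1 year (9.2.2). While the patient is on treatment, "Serum IgM, IgG and IgA" are also measured before every three-weekly cycle (9.2.1).

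**The concern.** Row 1 uses absence of progression as a stand-in for continuing response. The two are measured from different reference points: response from baseline, progression from the nadir. A patient can leave minor response and sit in stable disease, with a pre-cycle IgM on file that shows it, and still be scored as a responder on an older and better result.

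Minor response is the lowest category that counts towards the primary endpoint. The trial is single-arm and is decided on a fixed count, so each patient scored this way moves the count by one against the cut-off of 23.

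**Working it through.** **1. The plan's own design.** Section 17.1: "It is thought the response rate could be around 60% but a rate of more than 40% is needed". "Using an A'Hern phase II trial design with a 1-sided alpha of 0.05 and power of 80% we will require 42 patients", with success at 23 or more responses. An exact binomial search for the smallest design that meets these limits returns n = 42 with cut-off 23:

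- P(X ≥ 23 | n = 42, p = 0.40) = 0.0375
- P(X ≥ 23 | n = 42, p = 0.60) = 0.803
- For comparison, a cut-off of 22 gives P(X ≥ 22 | 42, 0.40) = 0.0706

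The stated sample size and cut-off are reproduced.

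**2. When a response can be lost without progression.** Let the nadir be a fraction f of baseline.

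- Response is lost when IgM exceeds 0.75 × baseline.
- IgM progression starts at 1.25 × f × baseline.
- There is a gap between the two only if 1.25 × f > 0.75, that is f > 0.60, or a best reduction below 40%.
- A minor response needs a reduction of at least 25%, so the group is patients whose best reduction was 25% to under 40%.

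With a best reduction of 40% or more, IgM reaches the progression level no later than it loses response, and row 3 applies once progression is confirmed and reported.

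**3. A record that row 1 would score as a response (invented figures).**

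| Time | IgM | Against baseline | Against nadir | Appendix 3 category |
|---|---|---|---|---|
| Baseline | 40 | – | – | – |
| Week 12 | 28 | 28/40 = −30% | – | Minor response |
| Week 21 (pre-cycle 8) | 33 | 33/40 = −17.5% | 33/28 = +17.9% | Stable disease on IgM, if no new signs or symptoms |
| Week 24 | missing | – | – | Row 1: responder |

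Response is lost above 0.75 × 40 = 30. Progression would need 1.25 × 28 = 35. The value of 33 lies between them.

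**4. Effect on the decision rule, if the endpoint is response at 24 weeks.** The number of such patients is an assumption, because the documents give no rate. Two ways of setting it:

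(a) k patients are certain to be scored as responders after losing response, and the other 42 − k respond with probability 0.40. The chance of success is P(Bin(42 − k, 0.40) ≥ 23 − k).

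| k | Chance of success |
|---|---|
| 0 | 0.0375 |
| 1 | 0.053 |
| 2 | 0.074 |
| 3 | 0.102 |

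(b) A share q of all patients is affected, so the scored rate is 0.40 + q. The chance of success is P(Bin(42, 0.40 + q) ≥ 23).

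| q | Chance of success |
|---|---|
| 1% | 0.0499 |
| 2% | 0.065 |
| 3% | 0.084 |

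**5. The opposite error in row 2.** Take a patient not in response at week 12 who first responds after it and then misses week 24. With no earlier response reported, row 2 scores non-responder. One row-1 error and one row-2 error together leave P(Bin(40, 0.40) ≥ 22) = 0.039, close to the design value.

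**The case against.** **The estimand is unsettled.** Chapter 17 says *by* 24 weeks. If that means ever responded, a lost minor response counts anyway, row 1 is right, and row 3 is the odd row. A reader might infer from row 3 that the table must intend status at week 24. That does not follow, since row 1's credit for an earlier response fits *by* equally well. This objection stands, and the point is therefore conditional on *at*.

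**The group is narrow.** A patient must have a best reduction in the 25% to under 40% band, rise above 75% of baseline but stay below 1.25 × nadir, have no clinical progression, and miss week 24. On schedule, cycle 9 day 1 falls at week 24 (8 × 3 weeks), so a patient on treatment has IgM due under both 9.2.1 and 9.2.2. Patients who have stopped treatment are more likely to be missing, but sections 9.3 and 9.4 list no IgM for them, so often no later value would show the loss. This stands and limits the likely size.

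**A single pre-cycle IgM is not a formal response assessment.** Appendix 3 has other criteria and asks for confirmation by a second measurement. This stands as a constraint on the fix. It does not justify setting aside a later observed value altogether.

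**The plan already limits the problem.** The rule is prespecified, missing data are not expected to be a problem, and section 15.4 has sites try to re-contact patients lost to follow-up, or check their records, before the primary analysis. That check covers survival and progression; it does not ask whether response was maintained.

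**Conclusion.** The point holds in a limited form. If the endpoint is response *at* 24 weeks, as in sections 1.1, 3.1.1 and 3.2.1, row 1 can score as a responder a patient whose later IgM shows that a minor response was lost without progression. This can happen only when the best reduction was 25% to under 40%.

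The size is unknown and may be nil. One such patient would raise the chance of success at a true 40% rate from 0.0375 to 0.053, just over the stated 0.05. That figure assumes the patient occurs; if 1% of all patients are affected, it is 0.0499.

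A reader might infer more: that the missing-data table is biased only towards success, or that the trial's type I error will exceed 0.05. The documents support neither. Row 2 can err downwards, and no missing-data rate is given from which to forecast a breach. The reason to act is that the rule can contradict data already collected, and that a result near 22 or 23 responses could turn on it.

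**What to change.** Make one edit that covers both the endpoint wording and the table.

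1. State whether the endpoint is response *at* or *by* 24 weeks, and use the same wording in sections 1.1, 3.1.1, 3.2.1, 17.1 and 17.2.1.
2. If *at*: amend rows 1 and 2 so that a missing week-24 response is derived from the latest evaluable Appendix 3 assessment, including the pre-cycle IgM, within a stated window before week 24 (for example 3 weeks). Score non-responder if that assessment no longer meets response, or if there is none in the window. Apply the Appendix 3 criteria other than IgM as well, and say how an unconfirmed IgM is handled. The pre-cycle 8 sample may be drawn up to 3 days before week 21, which is 21 + 3 = 24 days before week 24, so word the window to include it.
3. If *by* means ever responded: row 1 stands, and row 3 must be reconciled with it.
4. In either case, add a sensitivity analysis that counts every missing week-24 response as non-response.

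The cost is a few lines of text and minor programming. The sample size, the cut-off of 23, the visits and the data collected do not change. The downside is that the response count may be slightly lower.

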12.2.2. Reporting of Serious Adverse Events (SAEs)

All SAEs that occur between the signing of informed consent and 5 months post last IMP administration (**or after this date if the site investigator feels the event is related to an IMP**) must be submitted to UCL CTC by email within **24 hours** of observing or learning of the event, using the trial specific SAE Report. All sections on the SAE Report must be completed. If the event is **not being reported within 24 hours** to UCL CTC, the circumstances that led to this must be detailed in the SAE Report to avoid unnecessary queries.

Exemptions from SAE Report submission

For this trial, the following events are exempt from requiring submission on an SAE Report **unless considered to be related to an IMP (rituximab and/or pembrolizumab)**. Exempt events must be recorded in the relevant section(s) of the trial CRFs:

- events that occur more than 5 months post last IMP administration. Note: this does not include pregnancy related events (see section 12.7)
- disease progression
- rituximab **infusion** reactions, unless life-threatening or fatal

Please note that hospitalisation for elective treatment, palliative care, logistical or socio-economic reasons does not qualify as an SAE.

[figure not shown]
**Completed SAE Reports must be emailed to UCL CTC within 24 hours
of becoming aware of the event
Email: [contact]**

SAE Follow-Up Reports

UCL CTC will follow up all SAE/SARs until resolution and until there are no further queries.

Sites must ensure any new and relevant information is provided to UCL CTC promptly. If an event term changes or a new event is added, the causality must be re-assessed by an Investigator. If the event is not being reported to UCL CTC within 24 hours, the circumstances that led to the delay must be detailed in the SAE/SAR Report to avoid unnecessary queries.

Adverse Event Reporting Flowchart

*This applies if AE, AESI, SAE and Urgent Events reporting periods differs.

SAE Processing at UCL CTC

On receipt of the SAE Report, UCL CTC will check for legibility, completeness, accuracy and consistency. Expectedness will be evaluated, to determine whether or not the case qualifies for expedited reporting, using the approved RSI (the list of expected adverse events in the IB for pembrolizumab and SPC for rituximab).

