15.3.2. Withdrawal of consent for data collection

If a patient explicitly states they do not wish to contribute further data to the trial their decision must be respected:

- The following CRFs must be submitted at the time of withdrawal:
 - Change of status form
 - All CRFs up to and including the date of withdrawal of consent
- Thereafter no further data should be submitted, with the exception of SAE reports as per section 12.2 (due to the regulatory requirement for oversight of IMP safety)

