15.4. Losses to Follow-Up

If a patient moves from the area, every effort should be made for the patient to be followed up at another participating trial site and for this new site to take over the responsibility for the patient, or for follow-up via GP. Details of participating trial sites can be obtained from the UCL CTC trial team, who must be informed of the transfer of care and follow up arrangements. If it is not possible to transfer to a participating site, the registering site remains responsible for submission of forms.

If a patient is lost to follow-up at a site every effort should be made to contact the patient's GP to obtain information on the patient's status.

At the time of loss to follow up, the following CRFs should be submitted:

- Change of status form
- All CRFs due up to and including the date of loss to follow up

If contact is re-established with the patient, further follow up forms should be sent, including notifications of progression. A death form should also be submitted if the site becomes aware the patient has died.

Prior to primary analysis and presentation/publication of the primary endpoint data, UCL CTC will ask sites to attempt to re-establish contact with patients who were lost to follow up and/or check hospital records for evidence of when the patient was last known to be alive and evidence of disease progression and death.

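### After data consent is withdrawn, the missing-data table can count an early responder as a week-24 responder by default, and it has no row for unknown vital status

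*Combined protocol and SAP*

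**What the plan says.** Section 17.2.1 handles a missing week-24 response with a three-row table.

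- **First row:** a response at an earlier time point and a week-24 clinical status of "Alive with no progression reported" make the patient a responder.
- **Second row:** no earlier response makes the patient a non-responder, whatever the status.
- **Third row:** progression or death makes the patient a non-responder, whatever came before.

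The section expects little missing response data, gives no rate, and plans no sensitivity analysis.

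Three other sections decide what the trials unit can know about such a patient.

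- **15.3.2 (withdrawal of consent for data collection):** forms up to the withdrawal date are due, and then "Thereafter no further data should be submitted, with the exception of SAE reports as per section 12.2".
- **12.2.2 (SAE reporting):** "the following events are exempt from requiring submission on an SAE Report", and disease progression is on that list unless it is considered related to a trial drug.
- **15.4 (losses to follow-up):** if a "patient is lost to follow-up at a site every effort should be made to contact" the GP. Before the primary analysis, sites are also asked to try to reach lost patients again or to search hospital records for survival and progression.

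The timing of the endpoint differs between sections. Sections 17.1 and 17.2.1 define response by week 24; sections 1.1, 3.1.1 and 3.2.1 define it at 24 weeks.

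**The concern.** The first row relies on the absence of a progression report. That absence is informative only if a progression would have been reported. Once data consent is withdrawn, an ordinary progression has no route to the trials unit, so the condition holds whatever happened to the disease. The rule then gives a favourable classification with no week-24 evidence behind it.

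The trial has one arm and a fixed success count. A patient wrongly placed in the first row can only add to that count, and no control arm shares the error. At stake are a modest upward bias in the primary response rate and, near the threshold, the go/no-go conclusion itself.

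Not having progressed is also different from still responding. Appendix 3 measures response from baseline and progression from the lowest nadir, so a patient can lose a minor response without meeting the IgM criterion for progression.

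**Working it through.** **Inputs (17.1).** The design has a "1-sided alpha of 0.05" and 80% power. On the target rate it says "It is thought the response rate could be around 60" (per cent), and on the lower bound "a rate of more than 40% is needed". It concludes "we will require 42 patients", with success at 23 responders or more. The documents give no missingness rate, so every rate below is an assumption.

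**1. The plan's own figure.** With X ~ Bin(42, p):
- P(X ≥ 23 | p = 0.40) = 0.0375
- P(X ≥ 23 | p = 0.60) = 0.8032

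The design reproduces and respects its 5% ceiling. It leaves 0.05 − 0.0375 = 0.0125 to spare.

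**2. Which row applies.** Take an early responder with no week-24 value.

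| Situation | What can reach the trials unit | Row that applies |
|---|---|---|
| Data consent withdrawn, known to be alive | SAE reports only; progression normally exempt | First row, by default: responder |
| Data consent withdrawn, vital status unknown | As above | None |
| Lost, later traced | Survival and progression from GP or hospital records | First or third, on evidence |
| Lost, known to be alive, nothing found on progression | No disease information | First row, by default: responder |
| Lost, vital status unknown | Nothing | None |

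**3. Average effect on the error rate.** Let d be the share of patients missing at week 24 with disease status unknown. Let l be the share of all patients who responded early but no longer respond at week 24. Treat the two as independent, and take a true week-24 rate of 40%. The counted rate is then 0.40 + d·l.

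| d | l = 5% | l = 10% | l = 15% |
|---|---|---|---|
| 2% | 0.0386 | 0.0398 | 0.0409 |
| 5% | 0.0403 | 0.0433 | 0.0465 |
| 10% | 0.0433 | 0.0499 | 0.0571 |

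Entries are P(X ≥ 23). Only the last corner exceeds 0.05. The ceiling is reached when d·l is about 0.10 × 0.10 = 1% of patients.

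**4. Conditional worst case.** Suppose exactly m patients had lost response by week 24 and are all counted as responders. The other 42 − m then need only 23 − m responses, so the error is P(Bin(42 − m, 0.40) ≥ 23 − m):
- m = 1: 0.0532
- m = 2: 0.0744
- m = 3: 0.1021

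**5. The boundary.** Each patient is worth 1/42 = 2.4 percentage points. The 90% Clopper-Pearson intervals are:
- 23/42 = 54.8%: 41.0% to 68.0%, which excludes 40%
- 22/42 = 52.4%: 38.7% to 65.8%, which does not

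**6. Losing response without progressing (illustrative values).** IgM falls from 40 to 29: 11/40 = 27.5%, a minor response. It then rises to 35. That is 5/40 = 12.5% below baseline, so the minor response is lost. From nadir it is 35/29 − 1 = 20.7%, below the 25% needed for progression by IgM.

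**The case against.** **The group is narrow.** IgM is measured before every three-week cycle (9.2.1). Progression must be reported within 72 hours (12.5), and forms up to the withdrawal date are still due (15.3.2). Stopping treatment does not end follow-up (8.11, 15.2). Refusing trial visits still allows collection from the notes (15.3.1). Lost patients are traced (15.4), and NHS/CHI numbers are held for registry follow-up (section 11). All of this stands and keeps the numbers small. None of it provides for learning of progression after data consent is withdrawn: tracing covers lost patients only, and section 11 does not say that registry follow-up captures progression or continues after such a withdrawal.

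**A reader might infer that the table counts every patient of unknown status as a responder.** It does not. The first row sits under week-24 clinical status and also requires the patient to be alive. Where vital status is unknown, the table is silent.

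**A reader might infer that the first row conflicts with the second.** It does not. Both carry the last observed response status forward. Preferring non-response for unknown status is a different choice, not the repair of a contradiction.

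**Under the by-week-24 wording, an early response might count anyway.** That is fair as far as 17.1 and 17.2.1 go. But the objective and the endpoint definition say at 24 weeks, and the third row cancels an earlier response after progression or death. The table therefore does not follow a pure by-week-24 reading, and the wording has to be settled together with the first row.

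**Conclusion.** The concern holds, as a gap in a rule whose expected effect is small. For an early responder who withdraws data consent and is known to be alive, the first row gives responder without week-24 evidence. The same follows for a lost patient known to be alive when tracing finds nothing on progression. With vital status unknown, the plan does not say what to do.

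Under the assumed 2–10% missing and 5–15% lost response, the error moves from 0.0375 to about 0.039–0.057 and passes 0.05 only in the most adverse combination. This rests on dropout being independent of loss of response; if the two are linked, the effect is larger.

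A reader might take 0.053, 0.074 and 0.102 as the trial's type I error. They are conditional on 1, 2 or 3 such patients having occurred, each having truly lost response, with 40% applied to the rest. The true rate over all 42 is then (42 − m) × 0.40/42 = 39.0%, 38.1% or 37.1%. The documents do not support the claim that the stated 5% is broken in expectation.

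The practical reason to act is the boundary: one patient separates 23 from 22, and with it the conclusion.

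**What to change.** In section 17.2.1, before the primary data are seen:

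1. Restrict the first row to patients whose disease status is documented at week 24 (within the 3-day window of 9.2.2) or later, with no progression and with the latest available IgM still at least 25% below baseline. The IgM condition is needed because documented freedom from progression alone would still pass the patient in step 6 of the working.
2. Add a row: earlier response, week-24 response missing, week-24 status unknown (data consent withdrawn, or lost and not traced) = non-responder. State that a patient with documented status who fails the IgM condition is also a non-responder, so that every case has a row.
3. Add a sensitivity analysis that counts every missing week-24 response as non-response.
4. Reconcile by week 24 (17.1, 17.2.1) with at 24 weeks (1.1, 3.1.1, 3.2.1).

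The cost is a few lines of text and possibly a slightly lower reported rate. If one true responder falls into the new row, power at 60% is P(Bin(41, 0.60) ≥ 23) = 0.7501 instead of 0.8032. With two it is 0.689 and with three 0.619. The error at 40% then falls to 0.027, 0.019 and 0.013. If the sponsor prefers to keep the first row as it stands, item 3 is the minimum, together with a stated rule for unknown vital status.
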